## **20 PROTOCOL ADHERENCE AND AMENDMENTS**

The Site Investigator and each sub-investigator must adhere to the protocol as detailed in this document. Only the Sponsor (USWM) may modify the protocol. All amendments that have an impact on subject risk or the study objectives, or require revision of the informed consent document, must receive approval from the DSMB and central IRB/individual site's IRB before their implementation.

## 21 QUALITY CONTROL AND QUALITY ASSURANCE

Following written standard operating procedures, study monitors will verify that the clinical trial is conducted and data are generated, recorded, and reported in compliance with the protocol, GCP, and applicable regulatory requirements. Reports on monitoring activities will be submitted to the Sponsor.

The Sponsor (USWM) will secure agreement from all involved parties to ensure direct access to all trial-related sites, source data/documents, and reports for the purpose of monitoring and auditing by the Sponsor, and inspection by local and regulatory authorities.

The CRO \_\_\_\_\_ will be the Data Coordinating Center and will implement quality control procedures in accordance with GCPs and their internal Standard Operating Procedures, beginning with the data entry system and generate data quality control checks that will be run on the database. Any missing data or data anomalies will be communicated to the site for clarification and resolution.

1. INTRODUCTION

This document details the statistical analysis of the data that will be performed by for the US WorldMeds, LLC study USWM-LX1-3003-1.

The proposed analysis is based on the contents of the Final Version of the protocol (dated 10-Aug-2012) and amendments 1 and 2 (dated 08-Mar-13 and 06-May-13 respectively).

The Clinical Study Report will be written by following the guidelines in the ICH E3 document.

The primary objective of this study is to investigate the efficacy, safety, and dose-response of lofexidine (2.4 mg or 3.2 mg per day) in reducing withdrawal signs and symptoms and facilitating completion of detoxification/extending treatment retention in subjects undergoing detoxification from short-acting opioids in a double-blind inpatient setting (Days 1-7) followed by an open-label inpatient/outpatient setting (Days 8-14).

It is hypothesized that a daily dose of either 2.4 mg or 3.2 mg lofexidine will achieve greater efficacy than placebo with respect to overall symptom relief over the first 7 days of opioid withdrawal (primary endpoint) and will increase the likelihood of subjects completing Days 1-7 of treatment (secondary endpoint). Further, safety measures in the 2.4 mg and 3.2 mg total daily dose groups will be compared descriptively to assess whether the lower dose results in fewer and less severe adverse events than does the higher dose.

2. SAMPLE SIZE

Treatment effect and subject variability with respect to SOWS-Gossop scores were estimated from the prior Phase 3 study (USWM-LX1-3002), using the random coefficients model planned for the present study and estimating the treatment effect of 3.2 mg lofexidine versus placebo with respect to area under the curve (AUC) based on the SOWS-Gossop scores from Days 1 through 7 (AUC(1-7)). It was assumed that the treatment effect of the 2.4 mg lofexidine dose will be three-fourths the treatment effect of the 3.2 mg dose. The table below shows the power to find a significant treatment effect for the comparisons of the two lofexidine treatments versus placebo, assuming a sample size allocation ratio of 3:3:2 (3.2 mg lofexidine : 2.4 mg lofexidine : placebo) and accounting for the sequential testing approach described in Section 6.1. The power to find a statistically significant effect of the 3.2 mg lofexidine dose with respect to AUC (1-7) is in excess of 90% with the planned total sample size of 600.

	Power (%) with Respect to AUC (1-7)		
Total Sample Size	3.2 mg Lofexidine versus Placebo	2.4 mg Lofexidine versus Placebo	
600	94.6	72.6	
550	92.6	67.6	
500	90.1	62.2	
450	86.8	55.7	

Effective: 14-Feb-13

Page 4 of 26

3. RANDOMIZATION

A prospective subject who meets all of the study inclusion criteria and does not meet any of the exclusion criteria may be randomized into the study. The final eligibility criterion is a score of at least 2 on the OOWS-Handelsman at Baseline.

A stratified randomization procedure will be used to separately allocate male and female subjects in 1 of the 3 treatment groups: 2.4 mg lofexidine, 3.2 mg lofexidine, or placebo.

Randomization will be implemented centrally, that is, take place across all investigational sites using an Interactive Web Response System (IWRS) managed by Once eligibility criteria are confirmed at the Baseline visit, site personnel will access the IWRS and complete randomization procedures. The system will assign a unique kit number for drug dispensation according to the randomization scheme. The subject number assigned at screening should be used throughout the study in all source documents and eCRFs.

4. INTERIM ANALYSIS

No interim analysis is planned.

5. STATISTICAL METHODS

5.1 Continuous

Continuous variables and ordered categorical variables not subject to censoring will be summarized with the number of non-missing observations, mean, standard deviation, minimum, 25th percentile, median, 75th percentile, and maximum. Continuous variables subject to censoring (e.g., time to removal from study treatment) will be summarized by the number of subjects with data, 25th percentile, median, 75th percentile derived from Kaplan-Meier estimates of probabilities.

For summary statistics, means, medians and percentiles will be displayed to one more decimal place than the raw data, dispersion statistics (e.g. standard deviation) will have two more decimal places, and the minimum and maximum will be displayed to the same number of decimal places as reported in the raw data.

5.2 Categorical

Unordered categorical and ordered categorical (depending on the number of categories) variables will be presented in contingency tables with cell frequencies and percentages for the number of non-missing observations and frequencies for the number of missing observations apart from disposition of subjects, concomitant medications, measurement of treatment compliance and adverse events where percentages will be presented for the population.

6. ANALYSIS PLAN

6.1 General

The treatment groups will be labelled as 2.4 mg Lofexidine, 3.2 mg Lofexidine and Placebo within the statistical output. In addition the 2.4 mg Lofexidine and 3.2 mg Lofexidine doses are

Effective: 14-Feb-13

Page 5 of 26

combined to form a single Lofexidine treatment group for presentation of safety data. Subject data in Appendix 16.2 listings will be ordered by treatment group, site and subject.

All statistical tests for efficacy will be 2-sided at the α =0.05 significance level.

All comparisons between the treatments will be reported with 95% confidence intervals for the difference. P-values will be rounded to four decimal places.

Only scheduled post-baseline laboratory and vital signs values will be tabulated. Post-baseline repeat/unscheduled assessments will be disregarded, although they will be listed in the relevant appendices to the report; in particular all clinically significant values will be noted.

All calculations and figures will be produced using SAS Version 9.3³ or higher.

All summaries and analyses documented below will be presented in the final integrated statistical/clinical report and tables that will be based on the E3 guidelines published by ICH. However, it is noted here that no analysis plan prepared in advance of the data can be absolutely definitive and so the final report may contain additional tables or statistical tests if warranted by the data obtained. The justification for any such additional analyses will be fully documented in the final report.

6.2 Derived Data

• Definition of baseline

For all variables, baseline is defined as the last non-missing value prior to the receiving the first dose of study medication.

All tabulations involving change from baseline data will only include subjects with cohort data i.e. with data at baseline and at follow-up. Change from baseline will be calculated as follow-up values minus baseline value.

• Incomplete dates

All incomplete dates will be included in the clinical database as they were entered in the eCRF. Thereafter for calculation purposes, the incomplete dates will be completed using pre-defined rules. If a day or month is not recorded it will be replaced by the first day of the month or January respectively, provided this does not contradict any other dates recorded. For missing adverse events and medications dates/times during the trial, the worst-case date will be used (e.g. the end of the month for a stop date and 23:59 for the stop time, the date/time of initial dose for start of AE i.e. all events with missing start dates will be assumed to be treatment emergent).

• Ambiguous values

In the case where a variable is recorded as ">x", " \geq x", "<x" or " \leq x", then for analysis purposes a value of x will be taken. Where a range of values is quoted the midpoint of the range will be taken.

Effective: 14-Feb-13

Page 6 of 26

• Questionnaire Data

In the event that component items used to calculate total scores for questionnaire data e.g. SOWS Gossop score are missing then the total scores will also be set to missing.

• Site pooling for statistical analyses

For the purposes of statistical analyses models where site is included within the model as a fixed effect, sites randomizing < 6 subjects will be pooled from smallest to largest until the pooled site subsequently created has at least 6 subjects. In the event that the pooling of sites with less than 6 subjects does not result in a site with > 6 subjects, then that pooled site with < 6 subjects will also be pooled with the next largest site with > 6 subjects. To break ties if more than one site has the same number of subjects, the site identifier will be used as a secondary sort key.

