All AEs will be listed and tabulated by severity, relationship to study medication, primary system organ class and preferred term according to MedDRA Version 16.0. In counting the number of events reported, a continuous event, i.e., an event reported more than once and which did not cease, will be counted only once with the worst recorded severity; non-continuous AEs reported several times by the same subject will be counted as multiple events. Events present immediately prior to the first dose of study medication that do not worsen in severity, will not be regarded as treatment emergent. Events with start dates more than 30 days after the administration of the last dose of study medication will not be considered treatment emergent and will be listed separately. In deriving the tabulation relating to preferred term reporting, the severity of a recurrent AE will be taken to be the most severe and the relationship to study medication as the highest probable.

The following will be summarized and presented for the overall population and by treatment group:

- The number and percentage of subjects experiencing at least 1 treatment emergent TEAE by MedDRA preferred term and SOC. A chi-squared test will be used to test for a difference in the percentage of subjects experiencing at least 1 TEAE between each of the 2 Lofexidine doses and placebo.
- The number and percentage of subjects experiencing an opioid withdrawal related TEAE by MedDRA preferred term and SOC.
- The number and percentage of subjects experiencing TEAEs by severity of event
- The number and percentage of subjects experiencing TEAEs by relationship to IP
- The number and percentage of subjects experiencing treatment-related adverse events (i.e. Possibly Related, Probably Related, Definitely Related)
- The number and percentage of subjects experiencing at least 1 treatment emergent SAE by MedDRA preferred term and SOC
- The number and percentage of subjects experiencing SAEs by severity of the event
- The number and percentage of subjects experiencing SAEs by relatedness to IP

Adverse events whilst receiving Lofexidine therapy during the open-label phase

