All AEs reported whilst receiving Lofexidine therapy will be listed and tabulated by treatment, severity, relationship to study medication, primary system organ class and preferred term according to Version 16.0 of MedDRA. In counting the number of events reported, a continuous event, i.e., an event reported more than once and which did not cease, will be counted only once with the worst recorded severity; non-continuous AEs reported several times

Effective: 14-Feb-13

Page 19 of 26

by the same subject will be counted as multiple events. Events present immediately prior to the first dose of Lofexidine during the open-label phase that do not worsen in severity, will not be regarded as treatment emergent. Events with start dates more than 30 days after the administration of the last dose of Lofexidine will not be considered treatment emergent and will be listed separately. In deriving the tabulation relating to preferred term reporting, the severity of a recurrent AE will be taken to be the most severe and the relationship to study medication as the most probable.

For data analysis purposes, all TEAEs for which data are missing regarding assessments of relatedness and/or severity will be defaulted to be assessed as being related and at the highest severity grade, respectively. Missing or incomplete TEAE start dates will be imputed to correspond with the date of dosing.

Narratives of deaths, serious and other significant adverse events will be provided in the relevant section of the CSR.

A complete subject listing of all adverse events will be provided in Appendix 16.2 to the study report. This listing will include treatment, AE verbatim, MedDRA primary system organ class and preferred term, the time of onset and cessation of event relative to first dosing of study medication, duration of AE (for ongoing AEs use the date of investigator signature as the cessation date for calculation purposes), whether serious, severity, relationship to study medication, action taken and outcome.

Treatment emergent and non-treatment emergent events will be listed separately.

Clinical Laboratory Evaluations

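### An adverse event with no start date is dated to the initial dose whatever the phase, so an open-label or follow-up event in a placebo completer who took lofexidine can be counted as a double-blind placebo event; the rules for incomplete start dates are unreconciled

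*SAP*

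**What the plan says.** Three rules bear on an adverse event's start date.

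- **SAP 6.2 (Derived Data, incomplete dates), missing start.** The worst-case value is "the date/time of initial dose for start of AE i.e. all events with missing start dates will be assumed to be treatment emergent". No phase is named.
- **SAP 6.2, partial dates in general.** "If a day or month is not recorded it will be replaced by the first day of the month or January respectively", as long as no other recorded date is contradicted.
- **SAP 6.13, after the open-label adverse event paragraph.** "Missing or incomplete TEAE start dates will be imputed to correspond with the date of dosing". Which dose is meant is not said.

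The start date then decides where the event appears. For the double-blind phase, SAP 6.13 ends the treatment-emergent window only after follow-up: "Events with start dates more than 30 days after the administration of the last dose of study medication will not be considered treatment emergent". The blinded comparison is inferential: "A chi-squared test will be used to test for a difference in the percentage of subjects experiencing at least 1 TEAE", each dose against placebo. For the open-label phase, the treatment-emergent count leaves out this class: "Events present immediately prior to the first dose of Lofexidine during the open-label phase that do not worsen in severity". Separately, "All AEs reported whilst receiving Lofexidine therapy will be listed and tabulated by treatment", which depends on when the event was reported.

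Protocol 10.1 makes completers in all three arms eligible for open-label lofexidine, and protocol 17.3 summarizes Days 8-14 by randomized group. Neither SAP addendum changes the start-date rules. Addendum 1 (Change 14) notes that the eCRF holds no open-label dosing dates, so open-label dosing is taken to begin the day after blinded dosing ends.

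**The concern.** Dating an undated event to the first dose is a sound conservative rule in a trial with one treatment period, because it keeps the event treatment emergent. Here the treatment changes at Day 8 for placebo subjects who continue, and the tables are split at that point. For those subjects the imputed date selects the drug to which the event is credited, and the rule selects placebo.

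Two outputs are at stake. One is the Days 1-7 incidence comparison of each dose with placebo. The other is the open-label treatment-emergent table, which shows what happens when former placebo subjects first take lofexidine; protocol 17.3.2 asks for new-onset events in that period.

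**Working it through.** The plan states no figure on this point, so there is none to reproduce. The check traces the rules, then sizes one event.

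**1. Fully missing start, placebo completer on open-label lofexidine.** Suppose dizziness is first reported on Day 10 with no start date.
- SAP 6.2 sets the start to Day 1.
- Day 1 lies in the double-blind phase, so the event is a placebo treatment-emergent event. This takes the double-blind table to be filled by start date, as its heading implies.
- With a Day 1 start the event precedes the first open-label dose. Under SAP 6.13 it is not treatment emergent there unless it worsens.
- It was reported during lofexidine treatment, so it is still listed and tabulated in that capacity.

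**2. How far onset can move.** From Day 14 to Day 1: 14 − 1 = 13 days. For an event first reported at the telephone contact 30 days after a Day 14 last dose: (14 + 30) − 1 = 43 days.

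**3. The same rule in a lofexidine arm.** An undated open-label or follow-up event also moves to Day 1. The drug is unchanged, but the event enters the blinded comparison on the lofexidine side.

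**4. Placebo completers who did not take open-label lofexidine.** A follow-up event within 30 days of the last dose is a placebo treatment-emergent event in any case, so the rule misattributes nothing.

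**5. Month known, day missing.** I applied the first-of-month rule to every onset day, for one first dose on each date of a 365-day year. This assumes Days 1-7 double-blind, 8-14 open-label and 15-44 follow-up.

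| True onset | Combinations | Lands before first dose | Double-blind | Open-label | Follow-up |
|---|---|---|---|---|---|
| Open-label | 365 × 7 = 2,555 | 64% | 23% | 13% | – |
| Follow-up | 365 × 30 = 10,950 | 14% | 15% | 20% | 51% |

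So the general partial-date rule does not always send an event to the initial dose. Where it lands before the first dose, a fallback is needed. SAP 6.13 treats incomplete starts differently. If its date of dosing is the first open-label dose, the event stays open-label. If it is the initial dose, the event goes to Day 1 and the recorded month is unused.

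**6. Size per subject.** Planned arms are 225, 225 and 150. One newly counted placebo subject adds 1/150 = 0.67 percentage points; five add 5/150 = 3.3. One newly counted subject in a lofexidine arm adds 1/225 = 0.44.

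An illustration with assumed counts for one event term (uncorrected chi-squared):
- 16/225 against 3/150: p = 0.027.
- One more placebo subject, 16/225 against 4/150: p = 0.061.
- Two more lofexidine subjects as well, 18/225 against 4/150: p = 0.031.

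A single reassigned subject can matter for an uncommon term, and movement in the active arms can offset it.

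**The case against.** The best defence is that the SAP 6.13 sentence already handles this. It follows a paragraph whose reference point is the first open-label dose. If its date of dosing means that dose, the Day 10 event is dated to about Day 8 and stays open-label. That reading is available, but the sentence does not say so, and SAP 6.2 would then assign the same event to another phase. The ambiguity stands.

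The second defence is that few events will be affected. Events are queried daily on Days 8-14 (protocol 15.5.1), a physician reviews them daily (16.7), and missing data generate site queries (18.2). This largely stands for Days 8-14. It is weaker for the single telephone contact 30 days after the last dose.

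The third is that the chi-squared test counts subjects, so a placebo subject already counted changes nothing. Withdrawal symptoms that subjects report can themselves be adverse events (protocol 15.4.8), which makes overlap plausible. This also stands, and it is why the size is given per subject newly counted.

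A reader might infer three stronger conclusions that the documents do not support:
- **That incomplete dates are all moved to the initial dose.** The general partial-date rule uses the first of the month or January.
- **That displaced events vanish from open-label reporting.** A non-worsening event loses treatment-emergent status only.
- **That the rule biases the comparison in lofexidine's favour.** Events move in all three arms, and nothing in the documents gives the balance.

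**Conclusion.** The point holds for completely missing start dates. SAP 6.2 as written credits an undated open-label or follow-up event to placebo in a placebo completer who took lofexidine and, unless it worsens, removes its open-label treatment-emergent status. In the lofexidine arms the rule brings such events into the double-blind comparison. The net direction of bias is not established. For incomplete dates, the finding is that SAP 6.2 and 6.13 conflict or are ambiguous.

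The size is 0.67 percentage points of placebo incidence per subject newly counted, with onset moved by at most 13 days (open-label) or about 43 days (telephone contact). This rests on the planned arm sizes, on allocation to phase by start date, and on SAP 6.2 governing missing starts. Because the documents give no frequency of missing dates, no total is offered. This is a minor correction to safety reporting and leaves the efficacy analysis untouched.

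**What to change.** Keep SAP 6.2's rules for stop dates, stop times and medications, and SAP 6.13's rule for missing severity and relationship. Replace only the adverse event start clause in 6.2 and the start-date sentence in 6.13 with one rule:

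- A missing or partial start is set to the earliest date consistent with the recorded date parts, the stop date and the visit of first report (where captured), and not before the last adverse event assessment without the event.
- The initial dose is used only if nothing places onset later.
- If the phase still cannot be determined in a subject who took open-label lofexidine, the event goes to the phase in which it was first reported, with follow-up reports assigned to open-label. The double-blind table is shown both ways.
- If the phrase date of dosing is kept anywhere in 6.13, say which dose it means.

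The rule should not add a floor at the first dose of the phase of first report. Such a floor would push a late Day 7 onset first recorded on Day 8 into open-label, the same error in reverse.

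The cost is SAP wording, minor programming and one extra sensitivity table. Confirm first that the database captures the visit of first report; the documents do not show that it does.

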6.3 Analysis populations

The **Enrolled Population** includes all subjects screened into the study irrespective of whether they received the study medication.

Three principal analysis populations are defined as follows:

- Intent-to-treat (ITT), consisting of all randomized subjects. Subjects will be assigned for analysis according to the group to which they are randomized.
- **Modified intent-to-treat (mITT)**, consisting of all subjects in the ITT group who received at least one dose of study medication. Subjects will be assigned for analysis according to the group to which they are randomized.
- **Safety** consisting of all subjects who received at least one dose of study medication. Subjects will be assigned for analysis according to treatment received.

The principal analysis population for the analyses of demographics and baseline characteristics and efficacy will be the mITT population. Sensitivity analyses of the completion status endpoint will be carried out using the ITT population.

Safety summaries will be provided for the Safety population.

Data recorded on subjects who are in the ITT but not in the mITT or Safety populations will be included in data listings.

